5.6 Data Analysis

Study Sample and Power Analysis

We aim for a total of 880 Veterans enrolled in the RCT (293/arm) based on power analyses provided below. Based on the study team's prior primary care-based studies with a similar recruitment approach, we anticipate 80% of patients approached to complete the index screen will participate. Based on pilot data from the Bedford MA VA where 78% of Veterans reported one or more needs, we then conservatively estimate that 50% of Veterans screened will report at least one of the nine unmet needs for which we will screen.

Thus, to yield a final sample of 880 Veterans with at least one unmet need enrolled in the study, we anticipate needing to approach 2200 eligible Veterans (733/site, or ~3 patients/day/site) i.e., of 2200, 80% (1760) will agree to participate in the study and of these, 50% (880) will have one or more unmet needs and be eligible for the RCT. If the participation rate or proportion of Veterans reporting at least one unmet need is lower than expected, we will increase the number of Veterans that we approach. We reviewed VA administrative data to determine the anticipated weekly count of Veterans eligible per site to participate in the study and there are more

than enough eligible Veterans to approach for additional screening if needed. We also anticipate drop-out rates at the 8-week follow-up survey to assess connection to resources and the 6-month unmet needs re-screen, respectively. Though the study team's prior study achieved a 65% follow up participation rate, here we conservatively anticipate a 50% participation rate for both the 8-week follow-up survey and the 6-month re-screen, reducing the sample for the three arms first to 440 Veterans total and then to 220 Veterans total.

Statistical Power for Aim 1: With a sample of N=1760 Veterans completing the index unmet needs screening, we will have 80% power to detect small effect sizes ($f^2=.01$; $OR=1.47$) using 2-tailed significance tests at the $\alpha=.001$ level if the intraclass correlation coefficient (ICC) (for the nesting of patients within sites) is negligible, or medium effect sizes ($f^2=.15$; $OR=4.07$) even if the ICC is as high as .02 for testing associations between the presence of each unmet need and sociodemographic, adherence, utilization, and clinical (BP only) variables. HbA1c is anticipated to be a relevant clinical outcome for only 40% of the sample; for HbA1c, we will have 80% power to detect small effect sizes ($f^2=.03$; $OR=1.84$) using 2-tailed significance tests at the $\alpha=.001$ level if the ICC is negligible.

Statistical Power for Aim 2: The power analysis for Aim 2 focused on the primary outcome of connection to resources to address unmet needs. The sample size was determined based on previous research outside VA which found that individuals who completed a screening and referral intervention were 15% more likely (adjusted Odds Ratio (aOR)=2.1) to have enrolled in a new community resource to address unmet needs post-referral compared to patients in the non-intervention arm. In the present study, we will have 80% power to detect an effect of this size (aOR=2.1) across the three arms using 2-tailed significance tests at the $\alpha=.05$ level, even if we assume an attrition rate as high as 50% for the follow-up phone call at 8-weeks post-screen (retained N=440 across all sites and arms) and a conservative ICC value for patients nested within sites of .01. Previous empirical work found ICC values <.0001 when adjusting for a small number of covariates (e.g., race, marital status) to examine new connections to resources to address unmet needs; we intend to collect and use these covariates in the present study as well. Assuming an ICC value of .0001, we will have 80% power to detect an effect as small as an aOR=1.7 if we assume a 50% attrition rate for the 8-week follow-up phone call, or as small as an aOR=2.0 if we assume a 70% attrition rate. We based our attrition rate upon the study team's prior study where Veterans

had low incomes, high unemployment and low educational status, yet only 35% were lost to a follow-up interview.

Quantitative Data Analysis

All data analysis will be conducted by study team members based in Boston. [name] is the study Data Analyst who will be responsible for developing the analytic data sets and all programming related to descriptive statistics and multivariate models. He will work closely with [name], the statistician who will be responsible for developing the statistical models and overseeing the overall analytic approach. All analysis will be conducted on VINCI.

Aim 1: Describe the prevalence and distribution of nine unmet needs (housing, food insecurity, utility insecurity, transportation, legal needs, employment, safety, social isolation, stress), and identify their associations with baseline sociodemographic characteristics, adherence, utilization and clinical outcomes.

Our primary analysis for Aim 1 will be descriptive. We will use data obtained during the index screening (N=1760) to generate descriptive statistics (e.g., proportions, 95% confidence intervals (CIs) to characterize the prevalence and distribution of each of the nine unmet needs at baseline across all study sites. We will next conduct inferential analyses to examine associations between unmet needs and sociodemographic characteristics as well as baseline outcomes (i.e., adherence, utilization, and clinical outcomes drawn from CDW data in the 12-months before the index screening for each Veteran). Hierarchical Linear Modeling will be used to control for the nesting of patients within sites, and patient-level variables will be treated as random effects. Hierarchical Generalized Linear Modeling (HGLM) will be used as appropriate to handle binary variables. Variables found to have statistically significant associations with unmet needs will be entered into multivariable models to better understand the correlates of each need. Bonferroni-corrected significance levels will control for multiple comparisons.

Aim 2: Compare the effectiveness of varying intensity referral strategies to address unmet needs on the primary outcome of connection to new resources to address unmet needs, and on secondary outcomes of post-intervention change in unmet needs, adherence, utilization, and clinical outcomes

Our primary Aim 2 analysis will compare *connection to new resources* at 8-weeks post-index screen (our primary outcome of interest) across the study arms. HGLM will be used to control for the nesting of patients within sites. In all models, patient-level intercepts and slopes will be treated as random effects. We predict significantly greater connection to new resources in the ASSISTANCE arm

compared to the SCREENING arm, with the AWARENESS arm falling intermediate to these other two study arms.

Adherence, Utilization, and Clinical Outcomes. We will also conduct a series of secondary analyses to examine whether the study arms influence more distal outcomes, including adherence, utilization, and clinical outcomes. Specifically, to assess the impact of our intervention on more distal healthcare outcomes, we will use a difference-in-difference approach to examine whether changes from baseline at 6-months and 12-months post-referral differ across the three arms of our RCT (N=880). A series of HLM/HGLM analyses with patients nested within sites will examine differences in change from baseline across arms for the adherence, utilization, and clinical outcomes. As with the other analyses, all models will treat patient-level intercepts and predictors as random effects. We will have 80% power to detect small-to-medium effects ($f^2=.05$; OR=2.28) across the three arms using 2-tailed significance tests at the $\alpha=.05$ level, even if we assume a conservative ICC value for patients nested within sites of .01. HbA1c is anticipated to be a relevant clinical outcome for only 40% of the sample and we anticipate missing HbA1c test data for 17% of these Veterans in the year following their index screen; thus, for HbA1c, we will have 80% power to detect small-to-medium effects ($f^2=.08$; OR=2.71) across the three arms using 2-tailed significance tests at the $\alpha=.05$ level, even if we assume a conservative ICC value for patients nested within sites of .01.

Unmet Need Reduction: Similar analyses will be used to examine differences across our three study arms in change from baseline in the proportion of unmet needs among the sub-sample of participants who complete the re-screening at 6-months post-referral. Among this sub-sample (N=220, assuming attrition rates of 50% at both the 8-week and 6-month follow-up phone surveys), we will have 80% power to detect a small-to-medium effect ($f^2=.09$; OR=2.94) across the three arms in terms of unmet need reduction using 2-tailed significance tests at the $\alpha=.05$ level, even if we assume a conservative ICC value for patients nested within sites of .01.

Differences in Intervention Effectiveness. In addition to examining how the S&R influences connection to new resources, we will conduct additional analyses to examine whether there is differential impact between the two referral arms (Awareness and Assistance) on connection to new unmet needs resources; unmet need reduction; and adherence, utilization and clinical outcomes among Veterans with certain unmet needs or with fewer unmet needs. While we predict that providing SW support (Assistance arm) will generally have a larger impact on outcomes than providing a Resource Sheet alone (Awareness arm), it would be beneficial to know if the Resource Sheet alone (or even the screening and

provision of generic list of resources) is sufficient to produce comparable changes in outcomes among Veterans with certain unmet needs or among Veterans with fewer unmet needs. If true, future implementation research could create tailored interventions that funnel the resources for more time- and cost-intensive referral strategies to only those Veterans who need it most.

Testing Conceptual Path. To the extent that we discover differences across intervention arms in any of our more distal outcomes, we will conduct exploratory analyses to test appropriate causal mediational paths as proposed in our conceptual model using a series of HLM/HGLM analyses (with patients nested within sites). That is, we will examine whether the impact of our intervention on more distal outcomes (e.g., BP) can be explained completely (or in part) by its impact on more proximal outcomes (e.g., connection to new resources, reduction in unmet needs). For example, if we find differences across study arms in reduction in unmet needs, we will test whether the effect of the intervention arm on reduction in unmet needs is mediated by the effect of the intervention arm on connection to new resources.

Examining marginal intervention effects over and above S&R occurring as part of usual care. Finally, given that Veterans may already be accessing resources for some unmet needs as part of usual care and related to existing screening for homelessness and food insecurity, we will conduct supplemental analyses to examine whether our intervention effects hold when controlling for use of VA SW services not attributable to the present intervention (e.g., services already being accessed separate from the study intervention). Although we will specifically be assessing connection to new resources following the S&R mechanisms in our three study arms, it is possible that individuals already connected to certain resources will be more likely to seek out additional support/resources (e.g., because they already have successful experiences using VA resources to meet certain unmet needs) or less likely to seek out additional support/resources (e.g., because they feel they already have the support they most need). Because VA screens for housing and food insecurity, Veterans may already be accessing resources for these. To examine whether the intervention has a significant impact on connection to new resources, unmet need reduction, and more distal health outcomes when controlling for use of VA SW services not attributable to the present study, we will conduct supplemental analyses that control for connection to resources associated with each of our nine unmet needs prior to enrollment in our intervention. Use of SW resources not attributable to our study will be measured via CPRS encounter forms, where SWs record encounters with patients, and from referral/consult documentation available in CPRS during the 12 months prior to the start of our intervention.

Qualitative Data Analysis

Aim 3: Identify barriers and facilitators to Veterans' connecting with resources to address unmet needs and getting needs met, and explore potential explanatory factors related to the relative success of each study arm.

Transcripts will be initially coded using a priori constructs consistent with our conceptual model (Anderson Behavioral Health Model). A directed content analysis approach, allowing for new themes to emerge will be used.¹⁷ As coding proceeds, new emergent themes will iteratively be identified, elaborated upon, and expanded based on team discussion.¹⁸ New coding definitions may also be refined, and existing categories split and combined in the development of the coding matrix. This iterative process will eventually evolve to a point where all the existing categories will be sufficient to cover all new interview material that is obtained. The qualitative data analysis will be conducted by 3 study team members ([name], [name], [name]) and inter-rater reliability will be established using the “check-coding” process.¹⁹ All coders will independently code the same interview transcripts, and initial reliability estimates between all pairs of coders will be computed. Coders will then meet to compare their coding, discuss areas of difficulty, and attempt to reach agreement. A new interview will then be independently coded by all, and the process will be repeated until a reliable level of agreement (>80%) is achieved across all coders.¹⁹ After coding is complete, code output will be analyzed to identify themes within and across sample strata. All coding and analyses will be conducted using NVIVO qualitative analysis software.

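### The Aim 1 claim of 80% power at OR 1.47 for each unmet need is close to a best case; with binary correlates of less common needs, power is far lower

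*Combined protocol and SAP*

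**What the plan says.** Section 5.6, under Statistical Power for Aim 1, starts from the screened cohort: "With a sample of N=1760 Veterans completing the index unmet needs screening". At the .001 level, and with a negligible ICC, "we will have 80% power to detect small effect sizes ($f^2=.01$; $OR=1.47"). The scope is wide: "for testing associations between the presence of each unmet need and sociodemographic, adherence, utilization, and clinical (BP only) variables". Two companion figures use the same alpha: "medium effect sizes ($f^2=.15$; $OR=4.07$) even if the ICC is as high as .02", and, for a smaller subsample, "for HbA1c, we will have 80% power to detect small effect sizes ($f^2=.03$; $OR=1.84"). The subsample size comes from the statement that "HbA1c is anticipated to be a relevant clinical outcome for only 40% of the sample".

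The recruitment paragraph of the same section sets the planning prevalence. Against 78% in a pilot, the authors "conservatively estimate that 50% of Veterans screened will report at least one of the nine unmet needs for which we will screen".

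No prevalence is given for any single need, no split for any correlate, and no formula for the odds ratios. The Aim 1 analysis text calls the primary analysis descriptive. It then plans association tests, with HGLM for binary variables, and carries the significant variables into multivariable models.

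**The concern.** Whether a given need is present is a yes/no variable, and the information in a comparison of Veterans with and without it depends on how many have it. One odds ratio for all nine needs can be right only if prevalence hardly matters or if all nine are about equally common. The plan's own any-need figure makes it implausible that all nine lie near the favourable end.

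Two uses of the results depend on this. Significance decides which variables enter the multivariable models, so true correlates of rarer needs would often be screened out for lack of power. The Potential Benefits part of section 5.1 also expects the study to show which needs matter most for outcomes, as a guide to targeting resources. If power differs several-fold between needs, a comparison by significance partly ranks them by how common they are.

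**Working it through.** **Inputs from section 5.6:** N = 1760; two-sided alpha .001; power 80%; ICC negligible or .02; three sites, so 1760/3 = 586.7 per site; HbA1c subsample 0.40 × 1760 = 704; any-need prevalence 50% (pilot 78%). **Assumed, because the documents give none:** single-need prevalences, outcome prevalences, and the mean number of needs k among affected Veterans.

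**1. Reproduce the plan's figures.** Use a noncentral F test with 2 numerator df and noncentrality λ = f2 × N, then d = 2f and OR = exp(d × π/√3).

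| Case | N used | λ for 80% | f2 = λ/N | OR | Plan |
|---|---|---|---|---|---|
| ICC negligible | 1760 | 19.74 | .0112 | 1.468 | 1.47 |
| ICC .02 | 138.4 | 20.70 | .1495 | 4.067 | 4.07 |
| HbA1c | 704 | 19.86 | .0282 | 1.839 | 1.84 |

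For the second row the design effect is 1 + (586.7 − 1) × .02 = 12.71, and 1760/12.71 = 138.4. For the first row, f = √.0112 = .1059, d = .2118, and exp(.2118 × 1.8138) = 1.468. The 2 df is inferred because it matches all three figures; 1 df gives 1.43, 3.67 and 1.76, and 3 df gives 1.50, 4.37 and 1.89.

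**2. Where prevalence drops out.** For a yes/no need with prevalence p, f2 = p(1 − p)d². This reduces to d = 2f only at p = 0.5. The conversion therefore builds in an even split without saying so.

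**3. What the 50% any-need figure implies.** No single need can exceed 50%, and all nine reach 50% only if every affected Veteran has all nine. Average prevalence per need is 0.5 × k/9: 11.1% for k = 2, 16.7% for k = 3, 22.2% for k = 4. At the pilot's 78% these become 17.3%, 26.0% and 34.7%.

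**4. Binary correlates.** Let p0 be the outcome prevalence without the need and p1 = OR × p0/(1 − p0 + OR × p0). The groups are n1 = 1760p and n0 = 1760 − n1. Power = Φ[(|p1 − p0| − 3.291 × SE0)/SE1], where SE0 uses the pooled proportion and SE1 the separate ones.

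Example, need 10%, outcome 25%: p1 = .3289, n1 = 176, n0 = 1584, SE0 = .0348, SE1 = .0370. Then (.0789 − 3.291 × .0348)/.0370 = −0.96, so power is 17%.

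| Need / outcome | Power at OR 1.47 | OR detectable with 80% power |
|---|---|---|
| 50% / 50% | 77% (76.5%) | 1.49 |
| 25% / 25% | 48% | 1.63 |
| 16.7% / 25% | 32% | 1.75 |
| 10% / 25% | 17% | 1.98 |
| 5% / 25% | 6% | 2.49 |

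Treating the need as the response, with a correlate split 50/50, gives the same picture: 74.5% power at 40% prevalence, 46.9% at 20%, 18.7% at 10%.

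**5. Continuous correlates such as BP.** One yes/no need is a 1-df contrast, so detectable d = (3.291 + 0.842)/√(1760p(1 − p)). This is 0.20 at p = 50%, 0.23 at 25%, 0.33 at 10% and 0.45 at 5%.

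**The case against.** The case for leaving the text alone has real content.

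- **No miscalculation.** All three odds ratios reproduce, and f2 does not depend on prevalence. This stands: the fault is an unstated condition on the OR, not an arithmetic slip.
- **Continuous variables are covered too.** A mean difference of d = 0.212, the equivalent of OR 1.47, reaches 80% power at about 31% prevalence with 1 df. An OR of 1.47 per SD of a continuous correlate reaches it at about 7%. A reader might infer that the claim holds only if every need is present in half of Veterans. The documents do not support that: continuous correlates need much less, and for binary correlates even 50%/50% gives about 77%.
- **The 50% is deliberately low.** Some needs may be common; Appendix I follows up stress from the middle response category. But even at the pilot's 78%, the average need is at 17% or 26% with two or three needs per affected Veteran.
- **Limited consequence.** The primary Aim 1 analysis is descriptive. The 1760 follows from RCT recruitment (880/0.5), so this OR sets no sample size. The plan also gives the much larger OR of 4.07 for ICC .02. All of this stands and limits the weight of the point. It does not make the 80% statement true for the less common needs.

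A reader might also infer that null results will be reported as excluding any OR above 1.47, or that the study cannot see effects twice that size. Nothing in the documents says the first. The second (2 × 1.47 = 2.94) is reached only in the rarest case examined, need 5% with outcome 10%, where the detectable OR is 3.0.

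**Conclusion.** The statement needs correcting as written. An OR of 1.47 with about 80% power describes a near-even split, yet the plan attaches it to each of nine needs while assuming that only half of Veterans have any. At the assumed single-need prevalences of 25%, 10% and 5%, with a 25% binary outcome, power at that OR is about 48%, 17% and 6%. A realistic detectable OR runs from about 1.6 to 2.5.

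These sizes rest on assumed prevalences and a negligible ICC. That all nine needs cannot plausibly sit near 50% rests on the plan's own figure. The f2 value stands, the problem is milder for continuous correlates, and neither the trial's sample size nor its primary outcome is touched.

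**What to change.** In Statistical Power for Aim 1, replace the single OR of 1.47 with a short table of detectable odds ratios by need prevalence (for example 50, 25, 10 and 5%) and outcome prevalence, plus the 1-df detectable d for BP at the same need prevalences. State the conversion used and that 1.47 applies only to a near-even split. Add that associations for less common needs will be interpreted through estimates and confidence intervals, not as tests with 80% power. No fixed prevalence cut-off is needed.

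The cost is a change of wording and a less favourable stated figure. No additional Veterans are required.

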In the Assistance arm, we will hire and train social workers (one per site) to support Veterans to connect with resources following a standard operating procedure informed by current VA SW practices. Following the index screen and provision of tailored Resource Sheets, the RA will offer and encourage Veterans in this arm to receive assistance from a SW. Veterans may choose to opt out, but if they assent, the RA will provide the Veteran with the name and phone number of the SW who will contact the Veteran within two business days of the index screen (making up to five attempts to reach the Veteran by phone). During this initial call, the SW will use a standardized bio-psychosocial assessment tool used by VA SW and proven motivational interviewing methods^{20, 21} to uncover details of the Veteran's unmet needs, identify barriers to resolving the unmet needs, and develop an action plan for the Veteran including how to overcome the identified barriers. In addition, following VA SW practice, the SW will call the resource(s) to which the Veteran has been referred to inform them the Veteran will be coming for services. The SW will conduct initial follow-up by phone one week after the interview/action plan development, with planned subsequent phone outreach every two weeks for up to seven weeks. At each call and as needed (i.e., if Veteran has not yet connected to services), the SW will again employ motivational interviewing methods with the goal of re-affirming the action plan or modifying it as needed. The SW will track and record all Veteran encounters in a research data base, including time spent, challenges and best practices identified.

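### The eight-week primary outcome may be missing for up to half of randomised Veterans, and section 5.6 gives no method for handling this or testing its effect

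*Combined protocol and SAP*

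**What the plan says.** Section 5.6 (Study Sample and Power Analysis) sets the size: "We aim for a total of 880 Veterans enrolled in the RCT (293/arm) based on power analyses provided below". On follow-up it says: "here we conservatively anticipate a 50% participation rate for both the 8-week follow-up survey and the 6-month re-screen". It adds as context: "Though the study team's prior study achieved a 65% follow up participation rate". The Aim 2 power statement then allows for an "attrition rate as high as 50% for the follow-up phone call at 8-weeks post-screen (retained N=440 across all sites and arms"). It also gives a detectable effect under heavier loss: "or as small as an aOR=2.0 if we assume a 70% attrition rate".

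Section 5.5 and Appendix J give one source for the primary outcome, the Veteran's own report to the research associate on the eight-week call. The Aim 2 analysis paragraph in 5.6 compares connection across arms with a hierarchical generalised linear model (HGLM) for patients within sites. It names no analysis set and no rule for Veterans without an eight-week answer.

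Other outcomes in 5.6 are described differently. The adherence, utilisation and clinical outcomes are to be analysed with N=880. Unmet need reduction is analysed "among the sub-sample of participants who complete the re-screening at 6-months post-referral".

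In Appendix A, Assistance Veterans who accept help get a first social worker call, a follow-up a week after the action plan, and then continued contact, "with planned subsequent phone outreach every two weeks for up to seven weeks". The other two arms have no such contact.

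**The concern.** Each Veteran contributes one binary primary outcome. There is no earlier measurement of it through which the HGLM could carry information about a Veteran who misses the call, so that Veteran drops out of the fit. Unless something is added, the headline comparison is made among responders, and randomisation does not guarantee that responders are comparable across arms.

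Arm-specific selection is plausible in this design. The social worker calls aim to bring about connection and run to about the time of the survey, so they could also change who answers it. The research associate who opens the allocation envelope also makes the outcome call. If connectors and non-connectors answer in different proportions in Assistance than in Screening, the comparison can show an effect that is not there or hide one that is. Comparing response rates by arm would not necessarily reveal this, because overall response can be equal while its make-up differs.

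**Working it through.** **Inputs from the documents.** 880 randomised, 293 per arm; 50% response planned, 65% in the prior study; target adjusted OR 2.1; two-sided 0.05 (all section 5.6).

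**Assumptions, not in the documents.** True connection rates and response rates by arm and outcome. I use a base rate of 30%, and also 21.5%. The latter comes from reading the cited 15% difference as percentage points alongside OR 2.1, which gives 21.5% against 36.5%. A higher pair, 63.5% against 78.5%, also satisfies this.

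**The plan's figures.** 880 × 0.50 = 440, and 440 × 0.50 = 220; both reproduce. Responders per arm: 440 / 3 ≈ 147. At 21.5% against 36.5% with 147 per arm, ignoring clustering, pairwise power is 81%, in line with the stated 80%.

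**Formula.** With true connection rate p and response rates rc (connectors) and rn (non-connectors), the rate among responders is

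p·rc / (p·rc + (1 − p)·rn).

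The odds among responders are the true odds times rc/rn. Hence

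observed OR = true OR × (rc/rn in Assistance) / (rc/rn in Screening).

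The OR is unbiased when rc/rn is the same in both arms, even if response depends on connection and overall response differs by arm. Two checks:
- 70%/40% in both arms leaves a true OR of 2.1 at 2.1.
- 60%/46% in Screening, with both rates multiplied by 1.2 in Assistance (72%/55.2%), leaves a true OR of 1 at 1.00.

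**A created effect.** True OR 1, p = 30%, about 50% response in each arm, 147 responders per arm, two-sided z-test:

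| Screening rc/rn | Assistance rc/rn | Observed rates | OR | Rejection |
|---|---|---|---|---|
| 50%/50% | 60%/46% | 30.0% v 35.9% | 1.30 | 19% |
| 50%/50% | 65%/44% | 30.0% v 38.8% | 1.48 | 35% |
| 50%/50% | 70%/42% | 30.0% v 41.7% | 1.67 | 55% |
| 55%/48% | 60%/46% | 32.9% v 35.9% | 1.14 | 8% |
| 60%/46% | 70%/42% | 35.9% v 41.7% | 1.28 | 18% |

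First row: 0.30 × 0.60 / (0.30 × 0.60 + 0.70 × 0.46) = 0.180 / 0.502 = 0.359, and OR = 0.60 / 0.46 = 1.30. At a 21.5% base rate the same response rates give the same ORs. Rejection across the first three rows is then 16% to 48%.

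**A hidden effect.** True OR 2.1 (21.5% v 36.5%), Screening 50%/50%. Assistance response of 40%/55.7% gives OR 2.1 × 0.400/0.557 = 1.51, and power falls from 81% to 33%. With 30%/61.5%, OR is 1.02 and power 5%.

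**At 65% response.** Base rate 21.5%, true OR 1, Assistance 85%/59.5% and Screening 65%/65%: OR 0.85/0.595 = 1.43, rejection 32%.

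**A tipping point.** At 50% response, suppose responders show 21.5% against 36.5% and Screening non-responders connect at 21.5%. The all-randomised difference is then zero if Assistance non-responders connect at (0.2146 − 0.5 × 0.3646) / 0.5 = 6.5%.

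**The case against.** Several points on the other side stand.

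- A reader might infer that the plan states a responders-only primary analysis. It does not. The 440 appears in a power statement, and 50% is a cautious planning figure. Only need reduction is expressly limited to completers. For the primary outcome, responders-only is the default that follows from a single outcome source and no missing-data method. Section 5.1 (Safety and Data Monitoring Plan) says that a Data Analysis Plan was submitted for Data and Safety Monitoring Board approval; it is not among these documents and may cover the matter.
- A reader might infer that bias follows once response depends on both arm and connection. The formula shows that this is not enough: the response-connection relation must differ by arm.
- A reader might expect the error to favour Assistance. The documents do not settle the direction. Veterans may decline the social worker, the survey caller is the research associate, and the motivational approach is repeated for Veterans not yet connected, which could raise response among non-connectors.
- The largest figures rest on no dependence at all in Screening. Half the dependence there cuts OR 1.30 and 19% to 1.14 and 8%.
- Section 5.6 intends to use covariates such as race and marital status. A model adjusting for them already deals with non-response explained by them, and imputation from baseline data alone may add little. Standard imputation also assumes response is unrelated to connection given the imputation variables, so only the tipping-point analysis addresses the illustrated mechanism directly.

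None of this supplies a method for the missing outcomes or a test of robustness.

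**Conclusion.** The concern holds as a gap in the plan with a plausible route to bias. It does not show that the result will be biased. As section 5.6 stands, the primary result would rest on those who answer the call: 50% of those randomised on the planning figure, 65% if the prior study's rate is matched. Nothing is specified to show how far the conclusion depends on the rest.

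The possible size is material against a target OR of 2.1. On assumed response patterns a null effect can appear as OR 1.14 to 1.67 with 8% to 55% rejection, and a true OR of 2.1 can shrink to between 1.51 and 1.02. These figures are illustrative: the documents give no response rates by arm or outcome and no control connection rate. If the ratio of connector to non-connector response is the same in every arm, this mechanism leaves the OR unbiased.

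**What to change.** In section 5.6:

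1. Define the primary estimand for all 880 randomised Veterans.
2. Estimate it by multiple imputation carried out by arm, or by inverse-probability weighting, using site, number and type of index needs, the Appendix I answers on help already received and help wanted, sociodemographics and Corporate Data Warehouse data.
3. Make an arm-specific delta (tipping-point) analysis a required part of the primary report, since imputation alone cannot address response that depends on connection itself.
4. Report response by arm and by baseline characteristics, and keep the responders-only model as a sensitivity analysis.
5. Treat six-month need reduction in the same way.

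Two optional sources of auxiliary information exist. Post-index social work encounters from the electronic record would need a small extra extraction, because 5.6 plans only the 12 months before the intervention. Appendix J items 1 and 2 could be repeated at six months, with connections dated to the eight-week window. The yield may be small, since the 880–440–220 cascade counts six-month completers as half of the eight-week responders.

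The cost is protocol wording, modest programming and somewhat wider intervals. If the Data Analysis Plan already covers this, 5.6 should be aligned with it.
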